6.4.4 Concomitant Therapy during the study treatment

Subjects who use oral contraceptives, hormone-replacement therapy, or other maintenance therapy should continue their use. Effective contraception is required while receiving Ibrutinib in combination with GA101 - Obinutuzumab. For women of childbearing potential and men, effective contraception is required while receiving GA101 - Obinutuzumab and for 365 days (12 months) after the last dose of the study drug.

All subjects will receive allopurinol 300mg by mouth daily for 3 days prior to and during the first cycle of treatment. Allopurinol will be continued for the first cycle until the investigator determines there is no longer a concern for hyperuricemia. Subjects allergic to allopurinol will not receive allopurinol.

Ibrutinib + GA101 – Obinutuzumab. University of California, San Diego

All subjects will receive premedication with glucocorticoid, acetaminophen and diphenhydramine prior to each dose of GA101 – Obinutuzumab as described in section 6.2.5.

Anti-viral prophylaxis will be given to subjects with CLL during treatment and for up to 2 months after completion of treatment.

Prophylactic antibiotics to prevent the recurrence of an infection diagnosed during treatment may be instituted for any subject if clinically indicated.

6.5 GUIDELINES FOR IBRUTINIB MANAGEMENT WITH SURGERIES OR PROCEDURE

Ibrutinib may increase risk of bleeding with invasive procedures or surgery. The following guidance should be applied to the use of ibrutinib in the perioperative period for subjects who require surgical intervention or an invasive procedure while receiving ibrutinib:

6.5.1 Minor Surgical Procedures

For minor procedures (such as a central line placement, needle biopsy, thoracentesis, or paracentesis) ibrutinib should be held for at least 3 days prior to the procedure and should not be restarted for at least 3 days after the procedure. For bone marrow biopsies that are performed while the subject is on ibrutinib, it is not necessary to hold ibrutinib for these procedures.

6.5.2 Major Surgical Procedures

For any surgery or invasive procedure requiring sutures or staples for closure, ibrutinib should be held at least 7 days prior to the intervention and should be held at least 7 days after the procedure and restarted at the discretion of the investigator when the surgical site is reasonably healed without serosanguineous drainage or the need for drainage tubes.

6.5.3 Emergency Procedures

For emergency procedures, ibrutinib should be held after the procedure until the surgical site is reasonably healed, for at least 7 days after the urgent surgical procedure.

7. CRITERIA FOR SUBJECT DISCONTINUATION

Subjects will remain on study for three years after completion of the last cycle of treatment or until they have progressive disease requiring further treatment or death.

Subjects who meet the following criteria should be discontinued from the study:

Ibrutinib + GA101 – Obinutuzumab. University of California, San Diego

- HBV Reactivation that is not responding to appropriate management and antiviral therapy as described in section 6.2.10, or subjects with evidence of HBV associated hepatitis with LFT abnormalities. Subjects who are carriers of hepatitis B at the time of discontinuation from study treatment will continue to be followed for clinical and laboratory signs of active HBV infection and for signs of hepatitis.
- Severe or life-threatening anaphylaxis or hypersensitivity reaction
- Progressive Disease: Subjects with PD will discontinue the study treatment but will continue in follow-up until the beginning of new treatment or death.
- Severe life threatening reactions to GA101 Obinutuzumab or Ibrutinib administration.
- Medical Prudence/Non-Compliance: The Principal Investigator may remove a subject from study any time deemed medically prudent to do so to assure the subject's health and welfare. A subject will also be removed from study to preserve the integrity of the investigation. The latter includes incidents in which the subject frequently misses study appointments needed to accurately assess response/adverse reactions, or is non-compliant with study directions provided by the investigator or study personnel. "Inevaluable" subjects will be replaced to meet target accrual.

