Based on this, we will use a Simon's two-stage optimal design in this study (Simon, 1989). The null hypothesis that the true overall response rate is 78% will be tested against a one-sided alternative. In the first stage, 10 subjects will be accrued. If there are 8 or fewer responses in these 10 subjects, the study will be stopped. Otherwise, 22 additional subjects will be accrued for a total of 32. The null hypothesis will be rejected if 29 or more responses are observed in 32 subjects. This design yields a type I error rate of 5% and power of 80% when the true response rate is 94%.

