10.4 REPLACEMENT OF SUBJECTS

For the safety run-in, subjects will be replaced if they withdraw from the study prior to day 28 of the first cycle for any reason other than withdrawal due to toxicity, progressive disease (PD) or death.

In the phase II, up to 3 subjects will be allowed to be replaced if they have not completed treatment response assessment and, if they withdraw from the study for any reason other than toxicity, progressive disease (PD) or death.

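### Section 7 replaces undefined 'inevaluable' subjects without limit while Section 10.4 caps Phase II replacement and bars it for toxicity, PD and death; if replacement is related to outcome, the type I error exceeds 5%

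*Combined protocol and SAP*

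**What the plan says.** **Section 7 (Criteria for Subject Discontinuation).** The bullet on medical prudence and non-compliance says that the investigator "may remove a subject from study any time deemed medically prudent to do so", for the subject's welfare. It also provides for removal to protect the integrity of the study, for example after repeated missed appointments. It closes with the statement that 'inevaluable' "subjects will be replaced to meet target accrual". No definition, number, phase or excluded reason is given.

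**Section 10.4 (Replacement of Subjects).** "In the phase II, up to 3 subjects will be allowed to be replaced if they have not completed treatment response assessment", provided that the withdrawal was not for toxicity, PD or death. The same three reasons bar replacement in the safety run-in.

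**Section 10.3.2 (Efficacy Population).** A treated subject with no efficacy assessment after baseline is left out. Section 3.1.1, in contrast, says that response is determined in all treated subjects.

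**Section 10.3.4 (Phase II operating characteristics).** "The null hypothesis that the true overall response rate is 78% will be tested against a one-sided alternative". On stage 1: "If there are 8 or fewer responses in these 10 subjects, the study will be stopped". A trial that passes stage 1 goes on to 32 in all, 22 of them in stage 2, and rejects the null at 29 or more responses. The stated type I error is 5%, with 80% power at a true rate of 94%.

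**The concern.** The two sections can give different denominators for the primary test. Someone following Section 7 could replace any number of on-study removals, for any reason. Someone following 10.4 would stop at 3 and would replace none that followed toxicity, PD or death.

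This matters because the trial is open-label and run at one centre, so removal is decided with knowledge of how the subject is doing. A subject doing badly is more likely to be a non-responder. If that subject is removed before assessment and replaced, a failure leaves the count. The final rule tolerates only 32 − 29 = 3 non-responses, so each one lost from the count has weight. Section 10.3.2 does not restore it, because a treated but unassessed subject is outside the efficacy population.

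**Working it through.** **Inputs (Section 10.3.4).** Null rate 0.78; alternative 0.94; stage 1 n = 10, continue at 9 or 10 responses; total n = 32; reject at 29 or more.

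**Step 1: reproduce the plan's figures.** The probability of rejecting at true rate p is

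P(X₁ = 9)·P(X₂ ≥ 20) + P(X₁ = 10)·P(X₂ ≥ 19), with X₁ ~ Bin(10, p) and X₂ ~ Bin(22, p).

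- p = 0.78: 0.2351 × 0.1081 + 0.0834 × 0.2542 = 0.0254 + 0.0212 = **0.0466**.
- p = 0.94: 0.3438 × 0.8576 + 0.5386 × 0.9602 = 0.2948 + 0.5172 = **0.812**.

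Both agree with the stated 5% and 80%. A search for the smallest expected sample size under the null, with error at most 5% and power at least 80%, returns this same design. The design is sound as stated, with 5.00 − 4.66 = 0.34 points of type I error to spare.

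**Step 2: model outcome-related replacement.** Let q be the fraction of would-be non-responders who are removed before assessment and replaced, with no responder replaced. The documents give no rate, so q is an assumption and is shown as a range.

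*No cap (Section 7 read as covering on-study removals).* The response rate among retained subjects becomes p′ = 0.78 / (0.78 + 0.22(1 − q)). For q = 20%, p′ = 0.78 / 0.956 = 0.816. Putting p′ into the formula of Step 1 gives the type I error.

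*Cap of 3 (Section 10.4's number, without its excluded reasons).* An exact recursion runs over subjects assessed, responses so far and replacements used. Each null non-responder is replaced with probability q until 3 replacements have been used across both stages.

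*Expected replacements with no cap, per 32 retained:* 32 × 0.22q / (1 − 0.22q).

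| q | p′ | Error, no cap | Error, cap of 3 | Expected replacements |
|---|---|---|---|---|
| 0 | 0.780 | 4.66% | 4.66% | 0 |
| 10% | 0.798 | 7.3% | 7.2% | 0.7 |
| 20% | 0.816 | 11.2% | 10.8% | 1.5 |
| 30% | 0.835 | 17.1% | 14.9% | 2.3 |
| 50% | 0.876 | 37.1% | 23.3% | 4.0 |

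With no cap, the error already passes 5% at q = 2% (5.1%).

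**Step 3: what the cap contributes.** Removing the cap adds 0.1 points at q = 10%, 0.4 at 20%, 2.2 at 30% and 13.8 at 50%. At low q the expected number of replacements is below 3, so the cap seldom binds. What drives the error is q itself, and the rule in 10.4 that acts on q is the bar on replacing toxicity, PD and death withdrawals. Section 7 lacks that bar. How far the bar would lower q cannot be calculated, because the documents do not split removals by reason.

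**Step 4: the null case.** If replacement is unrelated to response, retained subjects still respond at 0.78 and the error stays at 4.66%.

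**The case against.** The best defence is that the sections can be read together: Section 7 says in general terms that replacement happens, and 10.4, whose title is replacement, supplies the number and the exclusions. On this view the specific section governs, and silence on a cap is not a rule of no cap. That is a sensible way to resolve the conflict, but the protocol does not say so and neither section refers to the other.

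A second argument concerns the word 'inevaluable'. The sentence follows directly on subjects who miss visits needed for assessment, so it may mean only those who cannot be assessed. PD and severe reactions have their own bullets, with no replacement sentence. This part stands: extending the sentence to removals for medical prudence is a reading of an undefined term that shares a bullet with them, not stated text. Restricting the term to screen failures is less convincing. Section 9.1.2 has its own replacement sentence for those, and Section 7 concerns subjects already on study.

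Third, q is assumed, and most of the modelled inflation also occurs with a cap of 3. Both statements are correct. The figures show how sensitive the test is; they do not forecast its error.

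A reader might also infer that Section 7 lets toxicity drop out of the run-in DLT count. The documents do not support this. Section 10.2.1 makes the first 6 dosed subjects evaluable for DLTs. Section 10.2.2 keeps dosed subjects with a safety follow-up in the safety analysis even if they withdraw early. Section 11.4.1.1 makes every treated subject evaluable for toxicity.

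**Conclusion.** The inconsistency is real and bears on the primary Phase II test. Section 7 has no limit, no excluded reason and no definition; 10.4 has a limit and three excluded reasons; nothing says which governs. If Section 7 covers on-study removals and replacement favours non-responders, the type I error exceeds 5%: 7.3% to 37.1% with no cap for q from 10% to 50%, and 7.2% to 23.3% with a cap of 3. This rests on an assumed q, on no responder being replaced, and on the wider reading of 'inevaluable'.

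It would go too far to conclude that the stated 5% is wrong or that the trial will exceed it. The design reproduces at 4.66%, and replacement unrelated to response leaves it there. Nor would the cap in 10.4 be enough by itself; the larger protection comes from its barred reasons and from keeping unassessed treated subjects in the count. This should be corrected, but it does not invalidate the design.

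**What to change.** 1. Delete the replacement sentence from Section 7 and refer to 10.4 as the only replacement rule.
2. State in 10.4 that an investigator removal made because of toxicity related or possibly related to treatment, PD or death falls under its exclusions, whatever label the removal carries. The wording should not extend to every adverse event, since Section 11.2 defines adverse events without regard to drug relationship.
3. Amend 10.3.2 so that treated Phase II subjects who are not replaced under 10.4 and have no response assessment count as non-responders in both the 9-of-10 and the 29-of-32 rules.

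The first two are clarifications of wording. The third changes the analysis population. None alters the sample size, the treatment rules or the investigator's freedom to remove a subject. The cost is that a few more unassessed subjects count as failures, which lowers the chance of reaching 29 responses somewhat. Some risk remains, because up to 3 replacements for permitted reasons could still be related to outcome.

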8. CRITERIA FOR STUDY DISCONTINUATION

The study will be discontinued due to the following reasons:

- Lack of meeting statistical end point after Stage I accrual. See section 10.3.
- Excessive toxicity of the regimen with > 1 subject death that is considered related to the study medications.

9. CLINICAL AND LABORATORY EVALUATIONS

9.1 EVALUATIONS PRETREATMENT

9.1.1 Study Entry

Subjects who are interested in participating in this research will have the protocol explained to them by the principal investigator / co-principal investigators or one of the study coordinators. Potential subjects will be given the opportunity to review the informed consent form and have their questions/concerns addressed. After this, if the

Ibrutinib + GA101 – Obinutuzumab. University of California, San Diego

subject chooses to enter the study, a screening date will be arranged by one of the study coordinators.

9.1.2 Screening

Screening for this study will occur after the subject has signed the approved informed consent form and received a copy of the "Experimental Subject's Bill of Rights." Screening labs, diagnostic tests, and physical examination will be performed four weeks prior to beginning treatment. Subjects who do not meet the criteria for study after screening will be excluded and will be considered non-evaluable and therefore replaced to meet the proposed accrual.

9.1.2.1 Screening History and Physical Examination

- Complete medical and surgical history; AND
- Record current medications and past medical history including history of previous treatments for CLL; AND
- Record transfusion (PRBC and platelets) and supportive care (IVIG) history; AND
 - Record history of infections (frequency, severity, treatment); AND
 - Physical exam including vital signs (T, P, R, BP); AND
 - Measure and record lymph node, spleen, and liver size; AND
 - Determine performance status (ECOG) and tumor assessment

9.1.2.2 Screening Laboratory Tests

(To be performed within 28 days prior to treatment start date)

- HBsAg, HbsAb, HBcAb (IgG, IgM), HAAb and Hepatitis CAb. (If HBcAb is positive an HBV-DNA viral load qPCR test will be performed)
 - HIV serology
 - CBC, differential, platelet count, PT, PTT, INR; AND
- comprehensive metabolic panel including: Total bilirubin, AST (SGOT), ALT (SGPT), alkaline phosphatase, albumin, creatinine, BUN, total protein, fasting blood glucose, calcium, sodium, potassium, chloride, HCO3, phosphorus, LDH and uric acid; AND

Ibrutinib + GA101 - Obinutuzumab. University of California, San Diego

- Beta-2 microglobulin AND
- Quantitative immunoglobulin levels (IgG, IgA, IgM) AND
- Immunophenotyping of blood mononuclear cells: CD3, CD4, CD5, CD8, CD19, CD20.
- Absolute T cell count including CD3+, CD4+, and CD8+ populations; AND
- Serum Pregnancy Test (HcG levels) for FCBP (females of child bearing potential)

9.1.2.3 Screening Diagnostic Tests

- CT scan or MRI of the chest, abdomen and pelvis will be performed in order to assess disease status and confirm Rai stage. Images will be performed within 28 days of treatment initiation.
- Electrocardiogram (EKG) (within 3 months of treatment start) will be performed as clinically indicated, and the investigator will perform an overall interpretation.
- Unilateral (minimum) bone marrow aspirate and biopsy for flow cytometry and histologic staining (within 90 days of treatment start) to assess leukemia cell infiltration and leukemia cell immunophenotype
- FISH and interphase cytogenetics will be performed on all subjects prior to therapy to assess for subjects with common and high-risk CLL genetic abnormalities within 3 months of treatment start
- Assessment of leukemia cell expression of ZAP-70, CD38 and mutational status of IgVH (performed at anytime prior to therapy)

9.1.2.4 Pretreatment Cumulative Illness Rating Scale (CIRS)

The Cumulative Illness Rating Scale (CIRS) (http://eforms.moffitt.org/cirsqScore.aspx) will be assessed prior to therapy or may be scored retroactively based on clinic notes and laboratory assessments (Appendix 6) in order to meet the Inclusion criteria for participation in the study (See section 4.1).

9.1.2.5 Research Studies

Correlatives Studies will be performed at [name] laboratory at different time points during the course of cycle #1 in all subjects.

Ibrutinib + GA101 – Obinutuzumab. University of California, San Diego

About 40 ml of blood will be collected into BD Vacutainer® Cell Preparation Tubes (CPT) on days 1, 2 and 8 of cycle #1 to perform pharmacodynamics studies including but not limited to the following:

 Assessment of the chemokine and cytokine profile using plasma samples from the subjects and correlation of the results with the presence of Infusion-Related Reactions (IRRs).

9.2 EVALUATIONS DURING STUDY TREATMENT & FOLLOW UP

- Physical examination including vital signs, performance status, lymph node, spleen, and liver measurements, adverse event assessment, concurrent medications, and transfusion requirements will be recorded prior to each new cycle.
- CBC with differential, platelets, complete metabolic panel with uric acid, LDH, albumin, creatinine, BUN, total protein, calcium, sodium, potassium, chloride, phosphorus and HCO3 will be performed during the following dates of treatment and follow up.
 - Cycle 1 Day 1,2,4
 - Cycle 1 Day 8, 15, 22
 - Cycle 2 to 5- Day 1, 8, 15, 22
 - Cycle 6 Day 1, 8, 15, 22, 28
 - Two months after completion of therapy Response assessment evaluation.
 - After response assessment every 3 months for 9 months.
 - Every 6 months until initiation of new treatment for CLL, consent withdrawal or death.
- All subjects will return to the clinic on day 4 of cycle #1 for laboratory assessment in order to evaluate the risk for TLS. Those subjects with laboratory evidence of TLS will return to the clinic on the day 4 of the subsequent cycles to continue follow-up of laboratory parameters.
- Absolute T cell count including CD3+, CD4+, and CD8+ populations will be performed on the following dates:
 - At screening or on day 1 of Cycle 1.

Ibrutinib + GA101 – Obinutuzumab. University of California, San Diego

- Two months after completion of therapy Response assessment evaluation.
- End of study
- Pregnancy monitoring for women of child bearing potential before each dose of GA101 Obinutuzumab (not required more than once monthly).

9.3 EVALUATION OF RESPONSE TO TREATMENT

The response assessment will be performed at 2 months after completion of study treatment in order to satisfy IWCLL criteria. This evaluation will include the following:

- Physical examination including vital signs, lymph node, spleen and liver measurements, performance status, adverse event assessment, concurrent medications, and recording of transfusion of blood products; AND
 - Liver chemistries: (ALT, AST, total bilirubin and alkaline phosphatase)
- CBC with differential, platelet count, complete chemistry panel with uric acid, LDH, albumin, creatinine, BUN, total protein, fasting blood glucose, calcium, sodium, potassium, chloride, phosphorus and HCO3.
 - Beta-2 microglobulin, and quantitative immunoglobulin levels (IgG, IgA, IgM); AND
- Absolute T cell count including CD3+, CD4+, and CD8+ populations (frequency should be consistent with standard of care evaluations).
 - Chest, abdominal and pelvic CT scan or MRI to assess response.
- Unilateral bone marrow aspirate and biopsy will be performed using multiparameter (4 colors) flow cytometry and histologic staining.
 - FISH and interphase cytogenetics.
 - Serum Pregnancy Test (hCG levels) for FCBP (females of child bearing potential).

Ibrutinib + GA101 - Obinutuzumab. University of California, San Diego

9.4 EVALUATIONS EVERY 3 MONTHS FOR NINE MONTHS AFTER RESPONSE ASSESSMENT

After the response assessment (at 2 months after completion of study treatment), the initial follow-up evaluations will be made every 3 months during 9 months. These evaluations will include the following:

- Physical examination including vital signs, lymph node, spleen and liver measurements, performance status, adverse event assessment, current medications, and recording of transfusion of blood products.
 - Liver chemistries: (ALT, AST, total bilirubin and Alkaline phosphatase)
- CBC with differential, platelet count, complete metabolic panel with uric acid, LDH, albumin, creatinine, BUN, total protein, fasting blood glucose, calcium, sodium, potassium, chloride, phosphorus and HCO3.
- Beta-2 microglobulin, and quantitative immunoglobulin levels (IgG, IgA, IgM). Continue monitoring of quantitative immunoglobulins (IgG, IgA, and IgM) for up to 2 years after completion of therapy or until they return to baseline.
- Pregnancy monitoring for women of child bearing potential should continue with every follow-up evaluation until 12 months following the last dose of GA101 Obinutuzumab.
- Chest, abdominal and pelvic CT scan or MRI in those subjects with clinical or laboratory alterations that suggest disease progression based on IWCLL criteria.
- For subjects that maintain a CR, a MRD assessment in peripheral blood using multiparameter (4 colors) flow cytometry will be performed at 6 and 12 months in order to assess MRD.

